### **3.4. Sample size**

Seventy-five people (patients and companions):

- 45 patients assigned to three intervention groups, 15 in each group (see section 3.5).
- 30 companions: Since two of the groups will require a companion, 30 people will be enrolled to be with the participant throughout the intervention.

### **3.5. Intervention**

Before starting the intervention, the diabetes educator (DE) will explain the research study to the patients and answer their questions. Informed consent will be obtained from each participant and their companion prior to enrollment in the study. Baseline information will be taken, including demographic data, socioeconomic status, time of illness, treatment, chronic complications of diabetes and comorbidities, anthropometric measurements (weight, height, blood pressure), and laboratory measurements (baseline glycated hemoglobin): (Annex 1).

Previously, the DE will contribute to the preparation of materials on nutrition and physical activity for people with diabetes and will have a flipchart for use in the training sessions (Annex 2).

[figure not shown]
Patients will be randomized to one of the three interventions to be evaluated:

#### *Intervention 1: Individual Incentives.*

1. Participants will receive information about the study, specifying that they will receive a reward of 150 soles (about 25% of the minimum wage) at each meeting if they have managed to lose one kilogram in a two-week period. The meetings will take place every two weeks for three months.
2. An initial assessment will be made to determine their weight and the results of their HbA1c will be provided.
3. A plan will be made to determine how many kilograms they should have at each biweekly meeting (Annex 3).
4. Education on nutrition and physical activity will be provided.

5. A manual with information on nutrition and physical activity for people with diabetes interested in losing weight will be given, including tips for loosing weight and a weight loss plan for a two-week period (Annex 4). The DE will manage an "ideal" weight loss plan for the patient throughout the 3 months of the study.
6. They will be given a diary to enter their daily diet and physical activity. The information in this diary will be the starting point to discuss with the diabetes educator at each session about the barriers and achievements in the implementation of the weight loss plan (Annex 4).
7. In addition to the introductory meeting, they will attend seven follow-up sessions (See Figure 1) and a final one in which he/she will be rewarded with the same amount (150 soles) if he/she managed to lower their HbA1c by at least 1%.

**Figure 1: Patient route map**

*Intervention 2. Mixed incentives: Set up by researchers*

1. Participants and their companions will receive information about the study, specifying that they will receive a reward of 150 soles (about 25% of the minimum wage) at each meeting if they have managed to lose one kilogram in a two-week period. The meetings will take place every two weeks for three months. The reward will be divided 50% for the participant and 50% for the companion.
2. An initial assessment will be made to determine the patient's weight and the results of his/her HbA1c will be provided.
3. A plan will be made to determine how many kilograms they should have at each biweekly meeting (Annex 3).
4. Education on nutrition and physical activity will be provided orally and/or with the support of audiovisual material.
5. A tri-fold leaflet will be given to the companion to guide his/her support (Annex 5).
6. A manual with information on nutrition and physical activity for people with diabetes interested in losing weight will be given to the patient, as well as tips and the weight loss plan per fortnight. The diabetes educator will manage an "ideal" weight loss plan for the patient throughout the 3 months of the study (Annex 4).
7. They will be given a diary to enter their diet, which will be the starting point to discuss with the diabetes educator at each session about the barriers and achievements in the implementation of the weight loss plan (Annex 4).
8. In addition to the introductory meeting, they will attend seven follow-up sessions and a final one in which he/she will be rewarded with the same amount (150 soles) if he/she managed to lower their HbA1c by at least 1%.

*Intervention 3. Mixed incentives: Set up by participants*

1. Participants and their companions will receive information about the study, specifying that they will receive a reward of 150 soles (about 25% of the minimum wage) at each meeting if they have managed to lose one kilogram in a two-week period and if the companion supports the process by attending all the biweekly follow-up meetings. The meetings will take place every two weeks for three months. The participant and the companion must negotiate on the day of the meeting in which the reward is given how they will distribute the amount received, specifying that the maximum that one party can receive is 80% and the minimum 20% of the total amount.
2. An initial assessment will be made to determine the patient's weight and the results of his/her HbA1c will be provided.
3. A plan will be made to determine how many kilograms they should have at each biweekly meeting (Annex 3).
4. Education on nutrition and physical activity will be provided orally and/or with the support of audiovisual material.

5. A tri-fold leaflet will be given to the companion to guide his/her support (Annex 5).
6. A manual with information on nutrition and physical activity for people with diabetes interested in losing weight will be given to the patient, including tips for losing weight and a weight loss plan for a two-week period. The diabetes educator will manage an "ideal" weight loss plan for the patient throughout the 3 months of the study (Annex 4).
7. They will be given a diary to enter their diet, which will be the starting point to discuss with the diabetes educator at each session about the barriers and achievements in the implementation of the weight loss plan (Annex 4).
8. In addition to the introductory meeting, they will attend seven follow-up sessions and a final one in which he/she will be rewarded with the same amount (150 soles) if he/she managed to lower their HbA1c by at least 1%.

### **3.5 Outcomes**

At the end of the three months, a comparison will be made between the achievements in terms of (1) weight loss and (2) glycated hemoglobin to then assess through qualitative research whether the amount of money given was the right one to promote weight loss, the role of education in diabetes and the process assessment.

### **3.6 Recruitment process**

#### **3.6.1 Randomization and other processes**

The recommendations of the CONSORT statement [26] will be followed in the randomization process. An investigator who is independent of the research process and is not involved in its activities will be responsible for randomization. For this purpose, a randomization in blocks of 4 will be used using pre-coded sealed envelopes to conceal the allocation. This process will be carried out one week after signing the consent form and the initial assessment.

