## **Phase 2: Intervention**

The patient will be contacted within three days of signing the consent form and their participation will be confirmed. Then the participants will be randomized. Those participants in intervention group 1 should not bring their companion to any of the meetings while in the case of intervention 2 and 3, the companions should sign a commitment to support the patient during the weight loss plan and to share the reward.

Subsequently, all selected patients will fill out the "Personality Inventory" survey to collect data on non-cognitive skills. (See Annex 6).

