## **Phase 3: Weight loss follow-up**

The follow-up will be carried out by a professional person qualified as a Diabetes Educator who will be trained by the project staff to follow up the 45 patients and their companions.

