### **Arm1: Individual Incentives**

Participants will be required to come every 2 weeks to measure their weight and to collect a blood sample for glucose measurement with a glucometer. Weight will be measured in fasting conditions, using the same scale and at the same time as the previous visit.

Each participant will attend a total of 8 sessions (including the initial meeting). In sessions 2 to 7 the diabetes educator will weigh them to see if they reached the goal.

- ***If they reached the goal:*** They will be rewarded and asked about the actions taken to reach their goal. In addition, suggestions for improving their nutrition and diabetes management will be reviewed. For this purpose, the information entered by the participants in their diary will be used. They will also be asked about their physical activity, adherence to treatment and changes in their eating habits. If they have received a reward in the previous session, they will be asked about how they used that reward.

- **If they did not reach the goal:** They will be asked about the actions they took to lose weight and the main challenges in implementing them. For this purpose, the information entered by the participants in their diary will be used. Suggestions for improving their nutrition and diabetes management will be reviewed. They will also be asked about their physical activity, adherence to treatment and changes in their eating habits.
- The patient will fill out a diabetes self-management questionnaire at each session (See Annex 4).

In session 7, a blood sample will be collected to measure his/her Hba1c. The results will be given in session 8 (last session) in which he/she will be rewarded if his/her Hba1c has dropped at least 1% since the beginning of the study (See Annex 7).

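### One fixed block size, unmaskable arms and an uncontrolled confirmation step leave allocation concealment incomplete; the risk is small if randomisation truly lags consent, and it is cheap to close

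*Combined protocol and SAP*

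**What the plan says.** - **Allocation method (3.6.1):** "For this purpose, a randomization in blocks of 4 will be used using pre-coded sealed envelopes to conceal the allocation". Only one block size is given. An independent investigator, not involved in study activities, is responsible for randomisation, which takes place one week after consent and the initial assessment.
- **Timing as given elsewhere (3.6.2, Phase 2: Intervention):** the patient is contacted within three days of consent, "their participation will be confirmed. Then the participants will be randomized". The person who makes this contact is not named.
- **Arm sizes (3.4):** "45 patients assigned to three intervention groups, 15 in each group".
- **Educator before consent (3.5 Intervention):** "the diabetes educator (DE) will explain the research study to the patients and answer their questions".
- **Educator after allocation (Phase 3: Weight loss follow-up):** a diabetes educator "who will be trained by the project staff to follow up the 45 patients and their companions". For arm 1, "In sessions 2 to 7 the diabetes educator will weigh them to see if they reached the goal"; arms 2 and 3 have the same weighing.
- **Masking (Phase 2):** arm 1 patients come without a companion. In arms 2 and 3 the companion signs a commitment to support the patient and share the reward. The arm is therefore plain to anyone at the sessions.
- **Timeline (3.8):** recruitment runs in months 4 and 5, and intervention starts in month 5.

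The plan does not say whether envelopes are numbered, in what order they are used, who opens them, or whether the block size is withheld from recruiting staff.

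**The concern.** A sealed envelope hides the next assignment only if it cannot be worked out from the assignments already made. With one known block size and visible past assignments, the later places in a block become partly or wholly predictable. The independent investigator protects the making of the list but does not prevent that inference.

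Two points are left open. One is the confirmation contact, where a patient can still be confirmed or lost before the envelope is opened. The other is the order in which waiting patients receive envelopes. If staff could predict the next arm at either point, patients could end up in the arm thought to suit them, for example those with a more committed relative in a companion arm. The arms might then differ at baseline for reasons other than chance. Section 3.5 Outcomes and section 5.8.1 both compare weight and HbA1c between arms, and section 2 uses the results to design a later randomised trial.

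**Working it through.** **Inputs.** Three arms, 45 patients, 15 per arm (3.4: 3 × 15 = 45). Block size 4 (3.6.1). One site (3.2) and no stratification described, so one sequence is assumed. Recruitment over two months (3.8). Even enrolment is assumed: 45 / 8.7 weeks ≈ 5.2 a week.

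**Composition of a block.** Four places cannot be split equally among three arms (4/3 = 1.33), and 45/4 = 11.25 blocks. The documents do not give the composition, so I take two readings: (a) one arm, chosen at random in each block, appears twice; (b) the same arm always appears twice. Reading (b) gives 22/11/11 after 44 patients, which does not fit 15 per arm.

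**Nobody pending, reading (a).** The guesser knows the block size and every earlier assignment.

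- Place 1: 1/3.
- Place 2: after one A, the chance of B (or of C) is 5/12 and of A 1/6. Best guess 5/12.
- Place 3: the first two agree with probability 1/6 (best guess 1/2) and differ with probability 5/6 (best guess 0.6). 1/6 × 1/2 + 5/6 × 0.6 = 7/12.
- Place 4: with probability 1/2 an arm has already appeared twice and the last place is certain; otherwise it is 1/3. 1/2 + 1/2 × 1/3 = 2/3.

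Mean best guess = (4 + 5 + 7 + 8)/12 ÷ 4 = 50.0%. Certain = 0.5/4 = 12.5% (11 complete blocks × 0.5 = 5.5 of 45 patients).

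**Nobody pending, reading (b).** Best guesses by place are 1/2, 1/2, 7/12 and 1. Mean = (6 + 6 + 7 + 12)/12 ÷ 4 = 64.6%. Certain = (1/6 + 1)/4 = 29.2%.

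**With patients pending.** If L patients ahead in the queue have no known assignment yet, place k is only as predictable as place k − L (place 1 if none has been seen). For reading (a):

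- L = 1: (4 + 4 + 5 + 7)/48 = 41.7%.
- L = 2: (4 + 4 + 4 + 5)/48 = 35.4%.
- L = 3: 16/48 = 33.3%.

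Mean best guess, with the share certain in brackets (block rows by enumeration, single list by simulation):

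| Scheme | 0 pending | 1 pending | 2 pending | 3 pending |
|---|---|---|---|---|
| Block of 4, doubled arm random | 50.0% (12.5%) | 41.7% (0) | 35.4% (0) | 33.3% (0) |
| Block of 4, same arm doubled | 64.6% (29.2%) | 52.1% (4.2%) | 50.0% (0) | 50.0% (0) |
| Fixed block of 3 | 61.1% (33.3%) | 38.9% (0) | 33.3% (0) | 33.3% (0) |
| One permuted list of 45 | 43.7% (3.2%) | 42.2% (1.0%) | 41.5% (0.3%) | 40.8% (0.1%) |

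With 5 pending, the single list is still at about 40%. An undisclosed mix of blocks of 3, 6 and 9 gives about 55% with nobody pending, and about 4% certain, to a guesser who knows that those sizes are in use. The 50.0% for a block with the same arm doubled is what constant guessing of that arm achieves, without information from earlier assignments.

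**How many are pending?**

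- Phase 2 read alone, envelope opened directly after the contact: few or none at the confirmation step, so the first column applies.
- Contact on day 3 and randomisation on day 7: 5.2 × 4/7 ≈ 3 pending at the contact, so reading (a) is at chance.
- A newly approached patient: 5.2 × 3/7 ≈ 2 ahead under a three-day lag, about 5 ahead under a one-week lag. Reading (a) gives 35.4% and 33.3%.

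**The case against.** A reader might infer that the sealed envelopes are defeated outright and that the educator can steer enrolment from the first invitation onward. The documents do not support that, for these reasons:

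- **Invitation.** Screening (3.6.2) invites all patients attending the outpatient service. It also requires each to have a healthy adult willing to act as companion. Selective invitation is therefore not a route the plan leaves open. Steering by companion is weakened too, though degree of commitment can still vary.
- **Lag.** Under the one-week rule and steady enrolment, a newly approached patient has more than a whole block ahead in the queue, and past assignments say nothing under random doubling.
- **Visibility.** Intervention starts in month 5, so sessions reveal little or nothing during month 4. The overlap is month 5 only.
- **Actors.** No section says that the educator knows the block size, decides eligibility, makes the confirmation contact or handles envelopes. That one person fills both educator roles is also inferred, from the shared title.
- **Purpose.** This is an exploratory pilot whose general objective is to compare implementation processes.

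All of this stands and limits the point, but it does not close it. Steady enrolment is an assumption, and slow or bursty recruitment shortens the queue. The two timing statements conflict, and the Phase 2 wording can leave nobody pending at confirmation. No text fixes the order of the envelopes.

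**Conclusion.** Concealment is incomplete at two specific points: the confirmation contact and the order of envelopes. At worst, with nobody pending and staff who know the scheme, the next arm is guessed 50% of the time and known for 12.5% of patients if the doubled arm is random (64.6% and 29.2% if the same arm is always doubled). With the one-week lag and about 5 enrolments a week, random doubling leaves predictability near the 33% of chance.

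The size thus depends on which timing statement governs, on the pace of enrolment and on what staff know, and the documents settle none of these. Nothing shows that steering would occur, and the consequence in an exploratory pilot is limited, although weight and HbA1c are compared between arms. I rate this a cheap improvement. It is worth making because the list has to be redrawn in any case: under random doubling, blocks of 4 give exactly 15/15/15 with probability of only about 0.065.

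**What to change.** In section 3.6.1, before the first randomisation:

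1. Have the independent investigator replace the blocks of 4 with one permuted list of 45 numbered envelopes, 15 per arm. This also delivers the stated arm sizes.
2. Assign envelopes strictly in order of consent. The investigator opens each one only after participation is confirmed and recorded. A patient who declines at that contact is recorded and uses no envelope.
3. Keep the details of the scheme from recruiting staff.
4. Reconcile the timing in 3.6.1 with that in Phase 2 of 3.6.2, and say who makes the contact.

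Do not repair the block size to a fixed, disclosed block of 3: with nobody pending it is more predictable than the present scheme under random doubling (61% best guess, 33% certain). Undisclosed mixed blocks of 3, 6 and 9 are second best. They cut certainty to about 4% but leave best-guess success at about 55%.

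The cost is a few sentences and a new list from an investigator already named. There are two downsides. Arm balance is slightly looser if recruitment stops early. With several patients pending, the single list is also somewhat more guessable than short blocks (41.5% with 2 waiting and about 40% with 5, against 33% for blocks of 3), though almost never certain. The fixed envelope order and a real lag therefore remain the main safeguards.

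### Blocks of 4 cannot be balanced over three arms and do not divide 45, so the stated randomisation does not secure 15 patients per arm or 30 companions

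*Combined protocol and SAP*

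**What the plan says.** Section 3.6.1 (Randomization and other processes) assigns the task to an independent investigator and specifies that "a randomization in blocks of 4 will be used using pre-coded sealed envelopes to conceal the allocation". Section 3.5 (Intervention) has three arms: "Patients will be randomized to one of the three interventions to be evaluated". Section 3.4 (Sample size) sets the target as "45 patients assigned to three intervention groups, 15 in each group" and adds, for companions, "Since two of the groups will require a companion, 30 people will be enrolled", making 75 people in all. Under Phase 2 in section 3.6.2, "Those participants in intervention group 1 should not bring their companion to any of the meetings", so companions are needed only in arms 2 and 3.

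The document does not put an allocation ratio into words; 1:1:1 follows from 15 per group. It gives no composition for a block of 4, no varying block sizes, no strata, and no rule that closes an arm once it reaches 15.

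**The concern.** Blocking is used in a small trial to keep arm sizes equal. For three equal arms, that requires blocks of 3, 6, 9 and so on. A block of 4 leaves one place over after each arm has had one, and the protocol does not say who gets it. Whoever prepares the envelopes must invent a rule, and different rules give very different trials.

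Three things are affected. The first is the arm sizes behind the comparison of weight and HbA1c in section 5.8.1: with 15 planned per arm, a gap of 4 is about a quarter of an arm. The second is the companion count, which equals 45 minus the size of arm 1, so the enrolment total of 75 holds only if arm 1 receives exactly 15. The third is the later randomised trial that this pilot is meant to inform (section 2), into which an unworkable scheme could be carried.

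**Working it through.** **Inputs.** Block size 4 (section 3.6.1); three arms (section 3.5, Intervention); 45 patients, 15 per arm, 30 companions, 75 people (section 3.4); no companion at meetings in arm 1 (section 3.6.2, Phase 2).

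**The plan's own totals.** 45/3 = 15; 2 × 15 = 30; 45 + 30 = 75. Section 3.4 is consistent with itself.

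**The block size against those totals.**
- 4 = 3 × 1 + 1, so no complete block of 4 can be equal over three arms. The most even block is 2:1:1.
- 45/4 = 11.25, so there are 11 complete blocks (44 patients) and one patient in a twelfth.

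**Size of the effect.** The documents do not say how the fourth place is filled. Three fillings are assumed below, each with every arm once per block plus one extra place.

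*(a) Extra place to a random arm in each block.* After 11 blocks each arm has 11 patients plus the extra places it drew, and patient 45 is equally likely to fall in any arm. The arm sizes are therefore 11 plus a multinomial count of 12 draws with probability 1/3 each.
- P(15/15/15) = [12!/(4! × 4! × 4!)]/3^12 = 34,650/531,441 = 6.5%.
- Mean gap between largest and smallest arm: 3.37. P(gap of 4 or more) = 42.4%.
- Arm 1 = 11 + Binomial(12, 1/3) and companions = 45 − arm 1. P(exactly 30 companions) = P(Binomial = 4) = 23.8%. The central 95% range is 27 to 33 companions.

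*(b) Extra place always to the same arm.* After 44 patients the split is 22/11/11. Patient 45 joins the favoured arm with probability 1/2, giving averages of 22.5/11.25/11.25. 15/15/15 never occurs. If arm 1 is favoured, companions number 22 or 23. If arm 2 or 3 is favoured, arm 1 has 11 or 12 patients and companions number 45 − 12 = 33 or 45 − 11 = 34.

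*(c) Extra place rotated arm 1, 2, 3.* Over 11 blocks, arms 1 and 2 are doubled four times and arm 3 three times: 15/15/14 after 44 patients. Block 12 doubles arm 3, so patient 45 goes to arm 3 with probability 1/2 (15/15/15); otherwise the split is 16/15/14. Companions number 30 with probability 3/4 and 29 with probability 1/4.

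**Cost in precision.** Take the standard error of a mean difference between the two smallest arms, relative to 15 v 15: √[(1/n₁ + 1/n₂)/(2/15)]. Under (c), 14 v 15 gives 1.018 and equal arms give 1, an average rise of about 1%. Under (a) the average rise is about 3%. Under (b), 11 v 11 gives 1.168 and 11 v 12 gives 1.143, an average rise of about 16%.

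**Block sizes that work.** Five blocks of 3 and five of 6: 5 × 3 + 5 × 6 = 45 patients and 5 × 1 + 5 × 2 = 15 per arm, hence 30 companions. A single size of 3, 9 or 15 also divides 45 and balances every block. Sizes 6 or 12 alone balance each complete block but leave 3 or 9 patients in an incomplete last one.

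**The case against.** The arithmetic is not in dispute; the objections concern how much it matters.

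- **15/15/15 remains possible.** It can arise by chance or through rotation. This stands: the finding is that the procedure does not guarantee the planned sizes.
- **The departures may be small.** Under rotation no arm is more than one patient off target. Under a random extra place, all arms lie within 13 to 17 in about 73% of lists. The 22–23 split needs the same arm to be favoured every time, which nothing in the document suggests. This also stands, but the protocol does not select rotation either.
- **This is a feasibility pilot.** Section 3.1 describes it so, and there is no power calculation. Patients are still allocated at random, so unequal arms cost some precision and do not in themselves bias the comparison. This stands and limits the harm.
- **Companions are largely covered.** Screening in section 3.6.2 confirms before randomisation that each patient has someone willing to take the role, so a different arm 1 count changes head-count and logistics without leaving a patient unaccompanied. This stands.

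None of these points reconciles sections 3.4 and 3.6.1. The list-maker still has no rule to follow.

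**Conclusion.** The concern holds. A block of 4 cannot be balanced over three arms and does not divide 45, and nothing elsewhere in the document supplies an unequal ratio or a rule that would rescue the target of 15 per arm. The rule is wrong as written, beyond being short of detail.

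The size depends on an unstated choice. The chance of exactly 15/15/15 is 0% with a fixed favoured arm, 6.5% with a random one and about 50% with rotation. Companions could number anywhere from 22 to 34 across the fixed cases, 27 to 33 (central 95%) in the random case, and 29 or 30 with rotation. These figures rest on the three assumed fillings and on enrolment stopping at exactly 45. The consequence for a pilot with descriptive aims is modest. It should nevertheless be corrected before the envelopes are prepared, because allocations already opened cannot be rebalanced.

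**What to change.** In section 3.6.1, replace the blocks of 4 with permuted blocks of 3 and 6 in random order, allocation 1:1:1: five blocks of each size make 45 patients, 15 per arm and 30 companions. State the ratio in words, and keep the block sizes from the diabetes educator and enrolling staff. Any scheme that balances each block and totals 45 would cure the arithmetic; mixing sizes also makes the next allocation harder to guess. If an unequal block of 4 was intended, the protocol must give its composition and how the extra place is assigned, and section 3.4 must be revised to the arm sizes and companion count that follow.

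The cost is one phrase in the protocol, a regenerated list and new envelopes, with no extra patients or staff. Section 5.9 requires prior written Ethics Committee approval for an amendment, so a short submission is also needed. This assumes enrolment has not begun; if envelopes have been opened, the block composition actually used should be documented and the achieved arm sizes reported.
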